the BOLD signal as an indication of cerebral activation in response to various tastes (milkshake and tasteless) during two 9.6-minute runs and in response to sucrose and tasteless during two 9.6-minute runs. A run consists of multiple blocks of taste (milkshake or tasteless). One block is a series of 4 - 8 presentations of tastes or tasteless; Each presentation starts with a 0.75 cc delivery of liquid over 2 s followed by 7 s in which to swallow. Each taste block is followed by a rinse (0.75 cc deionized water). Before the start of a new block there is a rest period of 10 seconds. Blocks vary in length between 32 and 80 seconds and the order of blocks is counterbalanced across subjects. This design is modified from prior event-related designs so as to yield a 61% improvement in design efficiency (calculated by FMRIB's software library FSL), which we confirmed to lead to more extensive and more intense BOLD response. The data can be analyzed offline and used for experimental control variables. Next, two 6 minutes resting state runs will be collected. During these runs, participants will be asked to stare at a cross-hair on the screen. Finally, a diffusion tensor imaging (DTI) scan will be obtained over 5 minutes.

5. Participants will be then taken out of the scanner and given one oral dose of either 30 mg of Morphine, or 50 mg of Naltrexone or placebo. 60 minutes later, VS will be collected again and logged in to the VS sheet and participants will undergo another scanning session while receiving milkshake, sucrose or tasteless solutions as described in 3 and while at rest. DTI and structural imaging will not be repeated. Blood pressure and heart rate will be continuously monitored during scanning using the Biopac system. The same procedure will be followed for the same participants in two subsequent visits (Day 4 and Day 5). *The*

Figure 1. Schematic illustration of study design; the order is just one example for one participants; the interventions will be randomized in a double blind protocol.

visits will be scheduled within a period spanning 4 weeks but no two-treatment days will be scheduled less than 48 hours apart. The overall design of the study will follow the illustration in Figure 1. However, the order of the interventions (i.e. Morphine, Naltrexone or placebo) will be randomized. The scanning session after medication administration will last between 45-60 minutes. Participants vital signs and mental

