and neurological state will be monitored for an additional 2 hours post-scanning at an interval of one hour using the NIH Stroke Scale Neurological Assessment flow sheet (two assessments in total); after 2 hours, if participants mental and neurologic state and VS are stable they will be reminded about side-effects of morphine and naltrexone and released. Morphine sulfate half-life is 2-4 hours. By the time our participants leave the MRRC one to two half-lives would have passed and the blood level of morphine would have dropped 2 to 4 times relative to time at ingestion.

B. Description of the open label arm

The same procedures described in A will be used to study 15 CBP patients using an open label design except when participants are taken to the scanner. At that point both the experimenter and the participant will know that morphine 30 mg is being administered. In addition, this arm of the study will have one arm only.

4. Genetic Testing N/A

A. Describe

i. the types of future research to be conducted using the materials, specifying if immortalization of cell lines, whole exome or genome sequencing, genome wide association studies, or animal studies are planned.

No future research is planned with the materials. We will determine the presence or absence of candidate opiate activity-related genes after the subject has provided their saliva.

ii. the plan for the collection of material or the conditions under which material will be received

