fMRI Data Analysis: The following measures will be derived from brain data: (1) parameter estimates(PE) for milkshake (MS) minus Tls (tasteless) (MS-Tls) will be defined at the single subject level using general linear model (GLM), implemented in FSL toolbox⁵⁵; whole brain connectivity of Blood Oxygen Level Dependent (BOLD) signal, using both MS runs or resting state runs, will be calculated between each voxel, or region of interest (ROI), and every other voxel in the brain to obtain (2) functional connectivity *FC* of specific ROIs or (3) degree maps (DM). *FC* is a measure of the strength of connectivity between an ROI and the rest of the brain; degree *D* is calculated as the total number of connections above a specific correlation threshold between a voxel and all the other voxels in the brain; we will study *D* over a range of thresholds 0.25 < r < 0.65 ⁵⁶. *DM* identifies brain hubs (with high *D*) and therefore allows between groups comparison in the most densely connected areas ^{57,58}.

The design is a within subject repeated measures design with treatment (Morphine, Naltrexone and Placebo) being the repeated measure and groups (healthy control vs. pain patients) as a factor. We will use repeated measures ANOVA to find differences in brain response (i.e. (*MS-Tls*) or *D* or *FC*) and psychophysical ratings of milkshake. The repeated measures design is a powerful one because it does not suffer from between subject

NCT04342130

variability. According to the preliminary data we expect to see decreased response to MS in opiate treated back pain patients and decreased D and FC.

SECTION VI: RESEARCH INVOLVING DRUGS, BIOLOGICS, RADIOTRACERS, PLACEBOS AND DEVICES

If this section (or one of its parts, A or B) is not applicable, state N/A and delete the rest of the section.

A. DRUGS, BIOLOGICS and RADIOTRACERS

1. **Identification of Drug, Biologic or Radiotracer:** What is (are) the **name(s)** of the drug(s) biologic(s) or radiotracer(s) being used? Identify whether FDA approval has been granted and for what indication(s).

- Morphine has U.S. Food and Drug Administration (USFDA) approval for relief of moderate to severe acute and chronic pain for which use of an opioid analgesic is appropriate.
- Naltrexone has USFDA approval for treatment of alcohol dependence and blockade of the effects of exogenously administered opioids.

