Did the FDA approve this IDE as **Category A** (experimental/investigational) or as **Category B** (non-experimental/investigational)?

Who holds the IDE?

Non-Significant Risk (NSR) Device Study: A study of a device that does not meet the definition for a significant risk device and does not present a potential for serious risk to the health, safety, or welfare of participants. Note that if the HIC concurs with this determination, an IDE is not required.

6. Abbreviated IDE or Exempt IDE: There are abbreviated requirements for an IDE and there also are exemptions to the requirement for an IDE. See the criteria in the HIC Application Instructions, Section VI.B.4 at http://www.yale.edu/hrpp/resources/docs/100FR1aHICProtocol_Application_Instructions5-25-11.pdf to determine if these pertain to this study.

Abbreviated IDE or Exempt IDE – *If criteria set forth in the HIC Application Instructions are met, copy and paste the completed relevant section from the Instructions into this application.*

7. Investigational device accountability:

a. State how the PI, or named designee, ensures that an investigational device is used only in accordance with the research protocol approved by the HIC, and maintains control of the investigational device as follows:

Maintains appropriate records, including receipt of shipment, inventory at the site, dispensation or use by each participant, and final disposition and/or the return of the investigational device (or other disposal if applicable):

Documents pertinent information assigned to the investigational device (e.g., date, quantity, batch or serial number, expiration date if applicable, and unique code number):

Stores the investigational device according to the manufacturer's recommendations with respect to temperature, humidity, lighting, and other environmental considerations:

Ensures that the device is stored in a secure area with limited access in accordance with applicable regulatory requirements:

Distributes the investigational device to subjects enrolled in the IRB-approved protocol:

SECTION VII: RECRUITMENT/CONSENT AND ASSENT PROCEDURES

1. Targeted Enrollment: Give the number of subjects:

a. targeted for enrollment at Yale for this protocol_75

b. If this is a multi-site study, give the total number of subjects targeted across all sites____

2. Indicate recruitment methods below. Attach copies of any recruitment materials that will be used.

3. Recruitment Procedures:

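### Nothing in the plan keeps the six treatment orders balanced across the healthy and pain groups, and the model has no visit term; the cost is a few percent of precision, not a raised error rate

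*Combined protocol and SAP*

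**What the plan says.** All references are to the combined protocol and SAP.

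- **Allocation.** Section V, 3.A (Day 3 scan session, item 5) states: "However, the order of the interventions (i.e. Morphine, Naltrexone or placebo) will be randomized". The legend of the design figure there adds only that "the interventions will be randomized in a double blind protocol". No generation method, block size, stratification or holder of the list is given. The one statement about counterbalancing in that section concerns taste blocks inside a scan run, not drugs.
- **Visits.** Each person has three treatment visits: "The same procedure will be followed for the same participants in two subsequent visits (Day 4 and Day 5"). They fall within four weeks, and "no two-treatment days will be scheduled less than 48 hours apart".
- **Analysis.** Section V, 12 plans a repeated measures ANOVA with treatment "being the repeated measure and groups (healthy control vs. pain patients) as a factor". Neither visit nor order is named.
- **Numbers.** Section VII, 1 gives the total as "targeted for enrollment at Yale for this protocol_75". Section V, 3.B says that the same procedures "will be used to study 15 CBP patients using an open label design". The split between healthy and pain participants is not stated.

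**The concern.** Three treatments over three visits give six orders. If each person's order is drawn independently, chance will place morphine earlier, or directly after naltrexone, more often in one group than in the other. Healthy versus pain is a planned factor, so the group-by-treatment contrast is a natural target of the analysis. Any drift over visits (habituation to the scanner or the milkshake, for example) or any effect of the preceding drug then enters that contrast in proportion to the imbalance. The planned model has no term to take the drift out. Allocation cannot be redone after enrolment, whereas a restricted list is easy to prepare beforehand.

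**Working it through.** The plan states no balance, power or sample-size figure, so there is nothing to reproduce.

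**Inputs.** Total 75 and open-label 15 are from the plan. Assumptions: the 15 are part of the 75, leaving 75 − 15 = 60 in the crossover; the split is 30/30 unless stated; "simple randomisation" below means six equally likely orders drawn independently. Effects are in units of the within-person SD.

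**1. How uneven the orders become**

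- Naltrexone directly precedes morphine in 2 of the 6 orders, a share of 1/3.
- SD of the between-group difference in that share: √(2 × (1/3)(2/3)/30) = 0.122, about 12 points.
- A 20-point difference is 6 people of 30. Comparing two independent binomials (30, 1/3), this is reached in 13% of trials.
- The share taking morphine first has the same one-in-three probability. Over splits of 30/30, 24/36, 20/40 and 15/45, a 20-point difference in it occurs in 11% to 18% of trials.
- Exact equality of the six orders in a group of 30: 30!/[(5!)⁶ × 6³⁰] = 0.04%. The median gap between the most and least used order is 5 people.

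**2. What it does to the group-by-drug contrast (morphine minus placebo)**

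- The visit position of morphine minus that of placebo is ±1 in four orders and ±2 in two. Its variance is (4 × 1 + 2 × 4)/6 = 2.
- SD of the between-group difference in mean position: √(2 × 2/30) = 0.365 visits.
- With an assumed drift of 0.3 SD per visit, the contrast shifts by 0.3 × 0.365 = 0.110 SD.
- Standard error without drift: √(2 × 2/30) = 0.365. The same figure arises because a difference of two measurements also has variance 2.
- True standard error with drift under simple randomisation: √(0.365² + 0.110²) = 0.381.
- The drift also sits in the observed within-person differences, so the analysis estimates it: √(2 × (2 + 0.3² × 2)/30) = 0.381. The true and estimated standard errors agree.

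**3. Simulated comparison, 30 per group, drift 0.3, no visit term**

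| Allocation | True SE | Estimated SE | Type I error (nominal 5%) | Power at an assumed effect of 1.0 |
|---|---|---|---|---|
| Simple | 0.381 | 0.380 | about 5% | about 73% |
| Blocks of six | 0.364 | 0.380 | about 4% | about 74% |

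Blocking lowers the true standard error by about 4% (0.381/0.365 = 1.04). Without a visit term the residual still carries the drift, so the test becomes slightly conservative and the gain is not used. With blocks and a visit term, the drift leaves the residual and the standard error returns to the drift-free 0.365. With a visit term but no blocking, the average efficiency loss within a group is about 3.4% at 30 people, 5% at 20 and 7% at 15.

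**4. Preceding-drug effect**

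The plan gives no figure for one. If naltrexone directly before morphine changed the response by an assumed 0.5 SD, the contrast would shift by 0.5 × 0.122 = 0.061. The standard error becomes √(0.365² + 0.061²) = 0.370, about 1% more. At a full SD it is √(0.365² + 0.122²) = 0.385, about 5% more.

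**5. After blocking**

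Thirty people make five whole blocks, so the orders are equal at allocation. In sizes such as 15 or 20, they differ by at most one. With assumed random dropout from 30 people, the SD of the morphine-minus-placebo mean position in a group is:

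| Dropout | Blocked | Simple |
|---|---|---|
| 10% | 0.09 | 0.27 |
| 20% | 0.13 | 0.29 |
| 30% | 0.18 | 0.31 |

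The imbalance falls by about 67%, 54% and 43%, but not to zero.

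**The case against.** The strongest reply is that the plan is silent rather than wrong. Saying that order is randomised is compatible with permuted blocks. The research plan was written for a form that asks for non-technical language, and Section VI.A, 6 routes study medication through the hospital's investigational drug service, which could already hold a list. This stands: a reader might infer that simple randomisation is prescribed, and the documents do not say so. The figures above depend on that assumption.

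A reader might also infer that chance imbalance biases the group comparison or inflates false positives. It does not. Orders are drawn independently, so drift becomes part of the within-person variance that the analysis estimates, and the error rate stays near 5%.

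Nor do the documents show carryover. Doses are single, at least 48 hours apart, and Section V, 3.A gives a morphine half-life of 2 to 4 hours. No naltrexone half-life is given. Balancing the preceding drug is therefore a precaution.

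Finally, a pre-dose scan is taken at every visit and could absorb some drift. Section V, 12 does not say that it is used, so it cannot be counted on. What remains is an allocation method that is not stated, a visit term that is absent, and an inexpensive way to settle both.

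**Conclusion.** The point holds as a modest gap in specification and efficiency. Nothing stated balances the six orders within or between the healthy and pain groups, and the model has no visit term. Under simple randomisation with about 30 per group, order patterns will be visibly uneven. The cost is about 4% in the standard error of the group-by-drug contrast if response drifts by 0.3 SD per visit, and less if drift is smaller.

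Two stronger readings should be set aside. One is that blocking removes the problem altogether. That needs group sizes in multiples of six, no dropout, and the same drift and carryover in both groups. None of these is stated, and Section V, 3.A itself provides for cancelled sessions and disqualified participants. The other is to judge the size from 15 per group, where a 20-point difference would occur in 33% of trials. That means 30 crossover participants, which does not fit the roughly 60 that the enrolment figures imply. If the 15 open-label patients are additional to the 75, the groups are larger and the imbalance slightly smaller. Priority is low to moderate.

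**What to change.** Make two changes together.

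1. In Section V, 3.A, state that treatment order is allocated from a computer-generated, concealed list in permuted blocks of the six orders, prepared separately for healthy and pain participants and held by the investigational pharmacy.
2. In Section V, 12, add visit (first, second, third) as a factor in the repeated measures model. Blocking does not replace this term: the term takes visit drift out of the residual, while blocking evens out the preceding-drug patterns that the term cannot reach.

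The cost is one list per group and one more model term using two degrees of freedom. No extra participants, visits or scans are needed. A fixed block of six makes the last orders in a block guessable if the blind fails. This is minor, because everyone receives all three treatments, and it is a reason to keep the list away from the study team.

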Each participant will meet with [name] to go over the possible side effects of 30 mg of Morphine, 50 mg of Naltrexone and placebo given at one dose. [name] will go over the most common side effects and will emphasize the risk of altered mental status (e.g. sleepiness, drowsiness) after one dose of morphine. [name] is Yale trained psychiatrist and will collect psychiatric history on possible previous misuse of alcohol, illegal drugs and prescription drugs. Any subject with such previous history will be excluded from the study. In addition, each participant will be given a patient information sheet about each of the medications used in the study.

To avoid fatigue subjects will take a 5-minute breaks every 15-20 minutes. This session takes about 2 hours. If the subject meets all eligibility criteria we will schedule them for a Presupplementation session at The John B Pierce Laboratory.

Measurment of body fat composition:

We will measure body fat composition of our participants; body fat and body mass index can be confounding in our analysis given that brain response to food is different between obese and healthy weight participants³⁶. The BodPod body composition tracking system is an air displacement plethysmograph which uses whole-body densitometry to determine body composition (fat and fat-free mass). The BodPod is an egg-shaped pod that consists out of two chambers. The front, or Test chamber, is where the subject sits and is comprised of a seat that forms a common wall separating it from the rear, or reference chamber. During the brief data collection period of the volume measurement, the chamber door is secured by a series of electromagnets and a gasket. A diaphragm is mounted on the common wall, which oscillates during testing. This causes small changes in volume inside the chamber, of which the pressure response to these small volume changes is measured. This is done by measuring the interior volume of the empty BodPod chamber, then measuring it again when the subject is seated inside. By subtraction, the subject's body volume is obtained. Once the subject's mass and volume are determined, body density is calculated and the relative proportions of fat and fat-free mass are determined. Thus this procedure is entirely non-invasive. A complete test requires about 5

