- Upon arrival to the Magnetic Resonance Research Center (MRRC) participants a urine drug test will be obtained as well as Breath alcohol levels will be assessed with the Alcohawk Elite Breathalyzer. If any of these tests are positive the study will be cancelled. Next, vitals signs (VS)(blood pressure, heart rate, respiratory rate, pulse oximetry, and temperature). If the urine drug test is positive for opiates or methadone the study will be cancelled and the subject disqualified for this study.
- Participants with BP < 90/60 and/or heart rate < 60 will be excluded and the study will be cancelled. VS will be logged in to a VS sheet and kept with the participant paper record in our study binders. Mental and neurologic status will be assessed for a baseline using the National Institutes of Health (NIH) Stroke Scale Neurological Assessment flow sheet (see attached form).
- 3. Next 20 ml of blood will be withdrawn. All blood samples will be placed in pre-chilled test tubes, and centrifuged at 4 C and the plasma stored at -70 C until analyzed according to standard procedures in the YCCI Core Laboratory
- 4. Next, participants will be undergo fMRI scanning: fMRI session: Set up is as above for fMRI simulator in fMRI training. Prior to getting the subject into the MR-room all people involved with the study walk through a detector designed to detect metal objects. We will use a Siemens 3T Trio TIM scanner with a 32channel head-coil. A T1-weighted 3D MPRAGE sequence (4 minutes) will be performed to obtain a high-resolution anatomical image and echoplanar imaging will be used to measure

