Minimizing risk involved with administration of one oral dose of Morphine and Naltrexone

We will minimize the acute risk of administration of oral 30 mg Morphine or 50 mg of Naltrexone by carefully monitoring vital signs and mental status using neuro-checks every 60 minutes after the administration. In addition, the study physician [name] will always be present during the whole duration of the visit when either of these drugs is administered.

Minimizing risk involved with the questionnaires:

Should a subject meet diagnostic criteria for any psychiatric disorder [name] will refer them for treatment. If a participant appears to be distressed or fatigued during assessments, the assessor will halt the procedure and take a break. The session will only recommence when and if the participant reports feeling capable of continuing

Minimizing risks involved with the mock fMRI scanner

We will attempt to minimize any discomfort associated with the mock fMRI scanner by informing the subject about what to expect prior to participation and explaining to them the equipment, how it works, which parts are replaced for every subject and how we clean any components that are not. Subjects will be instructed to tell the experimenter if they feel any discomfort with the procedure so that the session can be terminated.

Minimizing risks involved with MRI

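### The risk-minimisation text promises hourly mental-status checks after dosing, but the visit steps name none before the participant goes back into the scanner at 60 minutes

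*Combined protocol and SAP*

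**What the plan says.** Section V.10, under the heading on morphine and naltrexone administration, says acute drug risk will be reduced by "monitoring vital signs and mental status using neuro-checks every 60 minutes after the administration". The clock there starts at the dose. The same paragraph keeps the study physician on hand throughout each dosing visit.

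The Day 3 steps in Section V.3.A give the working schedule:

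- On arrival, vital signs (VS) are taken. They are defined as temperature, oximetry, respiratory rate, heart rate and blood pressure. A separate sentence adds that "Mental and neurologic status will be assessed for a baseline", using the NIH Stroke Scale flow sheet.
- After the pre-dose scan and the dose, step 5 says "60 minutes later, VS will be collected again and logged in to the VS sheet and participants will undergo another scanning session".
- During that scan, "Blood pressure and heart rate will be continuously monitored during scanning". On its length: "The scanning session after medication administration will last between 45-60 minutes".
- VS and mental and neurological state are then followed for two further hours, "at an interval of one hour using the NIH Stroke Scale Neurological Assessment flow sheet (two assessments in total".
- Participants are released "after 2 hours, if participants mental and neurologic state and VS are stable".

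Section V.3.B applies the same procedures to the open-label morphine arm.

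**The concern.** The visit steps are what staff follow on the day. Step 5 tells them to take VS and scan. Because the protocol defines VS without mental status, and names the neuro-check separately whenever it wants one, step 5 cannot be read as including it.

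The timing matters. Participants may not be on opiate analgesics and must test negative for opiates. They receive 30 mg of oral morphine, the top of the 10-30 mg starting range given in Section VI. The physician at intake "will emphasize the risk of altered mental status (e.g. sleepiness, drowsiness) after one dose of morphine". At 60 minutes the participant returns to the scanner to swallow liquids lying down for 45-60 minutes. Just before re-entry is the last easy moment at which a change from baseline could alter what happens next.

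**Working it through.** **The stated count.** Two hours of follow-up at one check per hour gives 2 / 1 = 2 assessments. The figure is reproduced, so nothing is wrong arithmetically.

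**The stated scan length.** The post-dose scan repeats the taste and resting runs but not the structural or diffusion scans: 4 x 9.6 + 2 x 6 = 50.4 minutes of acquisition. This fits the stated 45-60 minutes.

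**Post-dose clock from the visit steps (dose at 0, no set-up time, since none is given).**

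- VS at 60 minutes, then the scan.
- Scan ends at 60 + 45 = 105 to 60 + 60 = 120 minutes.
- Release two hours later: 105 + 120 = 225 to 120 + 120 = 240 minutes.

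**Where the two listed neuro-checks fall.** The text gives an interval and a number, not clock times.

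- Reading A, one and two hours after the scan: 165-180 and 225-240 minutes. This is likelier, because release at two hours depends on mental and neurologic state.
- Reading B, at scan end and one hour later: 105-120 and 165-180 minutes.

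**What Section V.10 would require.** Every 60 minutes from the dose gives checks at 60, 120 and 180 minutes, and also at 240 if release is at 240. That is 3 to 4 checks.

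**Comparison, if the visit steps are taken as complete.**

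| | Section V.10 | Steps, reading A | Steps, reading B |
|---|---|---|---|
| Earliest post-dose neuro-check (min) | 60 | 165-180 | 105-120 |
| Delay against 60 min | 0 | 105-120 | 45-60 |
| Checks up to release | 3-4 | 2 | 2 |
| Named before scanner re-entry | yes | no | no |

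**Comparison, if Section V.10 is applied alongside the steps.** The 60-minute check is required and the delay is zero. What remains is that step 5 does not list it.

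**Age of the baseline.** The baseline check comes before the pre-dose scan, which has 4 + 4 x 9.6 + 2 x 6 + 5 = 59.4 minutes of acquisition. With the 60-minute wait after the dose, it is at least 59.4 + 60 = 119.4 minutes old when the second scan starts.

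**The case against.** The strongest reply is that Section V.10 is operative text in the same protocol and already requires a neuro-check at 60 minutes. The sentence with the count of two concerns an additional period after scanning, so the count most naturally applies to that window and does not cap all post-dose checks. This is right. A reader might infer that the protocol limits post-dose neuro-checks to two, or that the check will definitely come 45-120 minutes late. The documents do not support either; both hold only if the visit steps are exhaustive. The reply does not remove the defect, however: it concedes that a check is required at a point where the step sheet omits it.

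A second reply is that the neuro-check form is an attachment and the design figure is not shown, and either could carry the timings. This also stands. The finding is about the visible text.

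A third is that the participant is far from unobserved. The physician is present, VS at 60 minutes include oximetry and respiratory rate, blood pressure and heart rate are recorded throughout the scan, there is an intercom and an alarm, supine swallowing is tried out beforehand in the mock scanner, and release requires stability. It would be wrong to infer that participants are scanned unmonitored. But none of these is a recorded neuro-check compared with baseline, which is what Section V.10 promises.

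**Conclusion.** The inconsistency is real. The visible visit steps name no mental-status check between the dose and re-entry to the scanner, although Section V.10 promises one every 60 minutes from the dose. Its practical size depends on how staff combine the two sections. Followed alone, the steps put the earliest post-dose neuro-check at 105-120 or 165-180 minutes. Read with Section V.10, the gap is an omission from step 5. Both statements assume no scanner set-up time, and any set-up would move every time after 60 minutes later.

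It is a moderate-to-minor safety correction, given the safeguards already in place. It touches no endpoint, estimate or error rate. Nor does the inconsistency by itself call for a new rule on when the physician should cancel the scan; no section promises one.

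**What to change.** In step 5, ask for VS and an NIH Stroke Scale neuro-check at 60 minutes, compared with baseline, before scanning. Add VS and a neuro-check when the scan ends, at about 120 minutes, so that the hourly promise is met in substance. Keep checks at one and two hours after the scan. Replace the count of two with wording that makes clear it covers only those two later checks. If the form or the design figure already gives times, align them. The open-label arm inherits the change through Section V.3.B.

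Resulting schedule, assuming 5-10 minutes per check and no set-up: scan starts at 65-70 and ends at 110-130 minutes. Checks fall at 60, 110-130, 170-190 and 230-250 minutes, the last at release. The gap across the scan is 50-70 minutes (60-80 with an assumed 10-minute set-up), so checks are about hourly, not exactly hourly. If a strict 60 minutes is not intended, Section V.10 should say approximately hourly, with scan end replacing the 120-minute check.

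Cost per dosing visit: two neuro-checks, 2 x 5 = 10 to 2 x 10 = 20 minutes of staff time under that assumption, plus one set of VS. Existing staff and an existing form are enough. Scan start and release move 5-10 minutes later because of the 60-minute check. The scan-end check falls inside the two-hour observation period and adds no further delay.
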